#### **4.6. Prior and Concomitant Therapy**

All concomitant medications will be recorded in source documents from Visit 1 (Day 1) through Visit 6 (Day 57). After Visit 6, only those concomitant medications associated with AESI, MAAEs, and SAEs will be recorded. Details on concomitant medications to be recorded include the generic and/or trade name, indication, dosage, regimen, route of administration, and start and end dates of the medication.

The following concomitant medications are prohibited during the study; however, they must not be withheld by the treating physician if clinically indicated to treat a subject:

- Any investigational medicinal product other than the study product
- Administration of immunoglobulins or any blood products
- Administration of any long-acting immune-modifying drugs (e.g., infliximab or rituximab) or the chronic administration (defined as more than 14 days) of immunosuppressive medications (includes systemic corticosteroids at doses equivalent to  $\geq 0.5$  mg/kg/day of prednisone; the use of topical steroids including inhaled and intranasal steroids is permitted).

Use of any prohibited medication must be recorded in the CRF. Whether a subject who uses a prohibited medication will be included in the Per Protocol Population will be evaluated on a case by case basis.

#### **4.7. Treatment Compliance**

Eligible subjects will be randomly assigned to receive 2 doses of study vaccine or placebo as IM injections in the deltoid muscle on D1 (V1) and D29 (V3), and be assessed in clinic for safety and reactogenicity at 7 days after each vaccination (V2 and V4), for safety at 28 days after the second vaccination (V6), and for safety and immunogenicity assessments at baseline (V1), 28 days after the first vaccination (V3) and 14, 168 and 336 days after the second

vaccination (V5, V7, and V8, end-of-study [EOS] Visit).

## 4.8. Protocol Deviation

A protocol deviation is any noncompliance with the clinical trial protocol, GCP, site SOP requirements, or departure from applicable regulatory requirements. The noncompliance may be either on the part of the subject or the site team/PI.

Major protocol deviations are a subset of protocol deviations that may significantly impact the completeness, accuracy, and/or reliability of the study data or that may significantly affect a subject's rights, safety, or well-being. Examples of major protocol deviations may include: failure to obtain informed consent, failure to report SAEs, enrolling subjects in violation of key eligibility criteria designed to ensure a specific subject population, or failing to collect data necessary to interpret primary endpoints, as this may compromise the scientific value of the trial.

When appropriate, corrective actions and preventive actions (CAPAs) will be developed by the site to address deviations, and will be implemented promptly. These practices will be consistent with ICH E6 Guidelines.

## 4.9. Safety and Immunogenicity Variables

The following section describes the collection of safety and immunogenicity variables.

### 4.9.1. Safety Variables

#### 4.9.1.1. Reactogenicity Events

Refer to Section [3.3.2](#)

#### 4.9.1.2. Unsolicited Adverse Event

Refer to Section [3.3.3](#)

#### 4.9.1.3. Serious Adverse Event (SAE)

Refer to Section [3.3.8](#) for the definition of SAE.

#### 4.9.1.4. Severity of Adverse Event

Refer to Section [3.3.9](#) for the details describing severity.

#### 4.9.1.5. Causality of Adverse Event

Refer to Section [3.3.10](#) for details on determining causality.

### 4.9.2. Immunogenicity Variables

- The functional (neutralizing) humoral immune response elicited by each formulation of NDV-HXP-S, as measured by a SARS-CoV-2 pseudovirus-based neutralization assay (PNA)
- The Immunoglobulin G (IgG) immune response elicited by each formulation of

NDV-HXP-S against the S protein of SARS-CoV-2, as measured by enzyme-linked immunosorbent assay (ELISA)

## 5. SAMPLE SIZE CONSIDERATIONS

This Phase 1/2 study has a two-part selection design with group elimination after the first part (i.e. Phase 1). A total of 25 ( $n_1$ ) subjects per group will be randomized across 4 candidates and one placebo group ( $n_1=20$ ) in the first phase. Assay titers will be analyzed on the log scale. The sample size and power calculations assume an interim analysis will be conducted after D43 of the first phase to eliminate two candidate groups by selecting the two groups with the largest means. Additionally, the observed seroresponse rate (defined as the percentage of subjects in a treatment group with at least a 4-fold rise from baseline in 80% neutralizing antibody titers) will need to be at least 52% at the lower limit of the 95% exact confidence interval. Based on this criterion, there is less than 10% chance of incorrectly failing to consider advancing a vaccine candidate with a true seroresponse rate of 85% or higher, which is estimated to be the minimum response rate that would be consistent with further investment in an additional second-wave COVID-19 vaccine. The Sponsor may consider other factors in selecting the two most suitable candidates to advance to second phase. In the second phase, 125 and 50 ( $n_2$ ) additional subjects will be randomized to the two candidate groups and the placebo group, respectively. The final analysis will be conducted on the full samples from the first and second phase ( $n_1 + n_2$ ).

**Safety:** Assuming 25 evaluable subjects per group in the first phase (and for elderly subjects enrolled in the second phase) and 150 total subjects ( $n_1 + n_2$ ) in the two candidate groups included in the second phase, the probability of observing at least one serious or severe adverse event by the underlying rate is shown in Table 7 in the protocol. If no events are observed, the upper bound of the exact 95% confidence interval would be 13.7% for the three eliminated groups and 2.4% in the two selected groups.

Immunogenicity: Groups with seroresponse below 52% at the lower limit of the 95% exact confidence interval will not be considered for selection for the second phase. This provides 90% power to correctly advance candidates with a true seroresponse rate  $\geq 85\%$ .

This is a two-stage selection design for selecting the group with the largest mean. Power for selecting the candidate with the largest true mean is driven both by the variability and the smallest difference between the highest mean and the means in the other three candidate groups.

Table 8 in the protocol shows the power to correctly select the candidate with the largest true mean in the first phase (to advance to the second phase) and the overall power for the Phase 1/2 by minimum fold-difference (on the titer scale) between the highest mean and the other means, assuming  $\log_{10}$  variability of 0.5. These calculations assume in the first phase there are  $n_1=22$  evaluable subjects in the four candidate groups, two groups are eliminated after the first phase, there are  $n_2=112$  additional evaluable subjects in the remaining two candidate groups at D43 of second phase ( $n_1 + n_2=134$ ), and  $\mu_4 > \mu_1 = \mu_2 = \mu_3$ .

## 6. GENERAL STATISTICAL CONSIDERATIONS

### 6.1. General Principles

All analyses will be tabulated by vaccination received, including a column for the total across all subjects. Baseline demographics and characteristics, including age, height, weight, sex, race ethnicity, and BMI will be summarized for both the exposed and per protocol populations by treatment group using descriptive statistics (mean, standard deviation, median, 1st and 3rd quartiles, minimum and maximum for continuous and frequencies, percentage, proportions, and exact Clopper-Pearson 95% confidence intervals (CIs) for categorical). All percentages will be presented to one decimal place.

Medical history will be listed and summarized by category. Using the WHO Drug Dictionary, concomitant medications will be tabulated by anatomical therapeutic chemical (ATC) classification, preferred drug name and treatment group. Medical history will be tabulated by MedDRA System Organ Class (SOC), Preferred Term (PT) and treatment group.

Summaries of subject disposition will be prepared for all subjects, including the number and percent of subjects screened, enrolled, study population of full analysis and per protocol, completed and not completed study within each study population, as well as a CONSORT diagram. The reasons for screen failures, abnormal with clinically significant of laboratory results, and COVID-19 associated symptoms will be summarized and listed.

A summary and listing of visit attendance will be prepared, in addition to a summary and listing of study product administration and sample collection/availability for each sample.

### 6.2. Timing of Analyses

Interim analyses will be performed after the last subject in the first phase has completed Visit 6 (Day 57) assessments and all the results are available. A final analysis on all safety and immunogenicity data will be performed after the study ends, when all additional safety and

immunogenicity data have been collected following the last subject's last study visit (Visit 7, Day 197), and the database is cleaned and locked.

### **6.3. Analysis Populations**

#### **6.3.1. Enrolled Population**

All subjects who provide written informed consent, regardless of the subject's screening, randomization, and treatment status in the study.

#### **6.3.2. Exposed Population**

All subjects in the enrolled population who were randomized and received at least one vaccination dose (i.e., were accrued).

#### **6.3.3. Safety Analysis Population**

All subjects in the exposed population for whom any safety data is available. All safety analyses will be performed using this population. The denominators for different safety endpoints may vary according to the number of subjects with available data for the specific endpoint. For instance, the solicited local and systemic adverse event endpoint will be based only on those who have the corresponding CRF data regardless of other safety data. Treatment groups for safety analysis will be assigned according to the actual treatment received.

#### **6.3.4. Full Analysis Population**

All subjects in the exposed population for whom any post-study product administration immunogenicity results are available. An immunogenicity analysis will also be performed using this population.

#### **6.3.5. Per Protocol Population**

All subjects in the exposed population who have no major protocol deviations that are determined to potentially interfere with the immunogenicity assessment of the study product.

This population will serve as the primary analysis population for the immunogenicity endpoints. The population will be adapted by time point to include all eligible subjects' data up to the time of disqualifying protocol deviation. The criteria (e.g., intake of prohibited medication expected to influence the immune response) for exclusion of subjects from the per protocol population, and determination of any exclusions based on a blinded review of the data, will be established before database freeze and lock for both interim and final analyses, respectively.

### **6.4. Covariates and Subgroups**

No covariates will be used in the analyses. No subgroup analyses will be performed in Phase 1.

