#### **3.1. Study Hypotheses**

The study will test the hypotheses that the NDV-HXP-S vaccine (NDV-HXP-S) have an acceptable safety profile and be well-tolerated at all dose levels when administered as a two-dose regimen either without adjuvant (at 1 µg, 3 µg, and 10 µg of S protein per 0.5 ml dose), or with the adjuvant CpG 1018 (at 1 µg of S protein per 0.5 ml dose) and to test that NDV-HXP-S elicit a measurable and dose-dependent neutralizing antibody response.

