#### **4.4. Method of Assigning Participants to Treatment Groups (Randomization)**

The randomization scheme was generated and maintained by Center of Excellence for Biomedical and Public Health Informatics (BIOPHICS).

Randomization for Part 1 (Phase 1) will be conducted after accumulation of 120 eligible subjects. Randomization will be stratified by gender and age (less than 40 years old and 40 to 59 years old, with approximately 50% of subjects in each age stratum). This is to ensure the groups are as similar (homogenous) as possible to ensure the down-selection of formulations is not biased by differences in demographic characteristics of the groups (such as age and gender). Randomization details will be outlined in a Randomization Plan prior to study initiation.

Each group will be divided into two subgroups, a sentinel subgroup (n=6) and a larger subgroup (n=24) that includes the remaining subjects to be evaluated at that dose level (or for that formulation in the case of the one adjuvanted treatment group). Initially, a sentinel subgroup of 6 subjects will be randomized to receive NDV-HXP-S 1  $\mu$ g or placebo in a 5:1 ratio. Sentinel subjects will be monitored for reactogenicity and safety through Day 8 (Visit 2), including for the initial 24 hours post-injection in clinic. If the PSRT has no safety concerns based on blinded review of all safety data, including clinical laboratory results, through Visit 2, the second subgroup of 24 subjects will be randomized to receive NDV-HXP-S 1  $\mu$ g or placebo at the same ratio; on the same day, the sentinel subgroup (n=6) for the second dose level to be evaluated (NDV-HXP-S 3  $\mu$ g) can be randomized to receive study vaccine or placebo in a 5:1 ratio, and so on for the subsequent dose level and formulation (see [Table 2](#)). The same procedure will be used for the NDV-HXP-S 10  $\mu$ g and NDV-HXP-S 1  $\mu$ g + CpG arms for a total of n=25 in each active group and n=20 in the placebo group. Randomization will be stratified by age (less than 40 years old and 40 to 59 years old) and gender with approximately 25% of subjects in each age & gender stratum.

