## 9. IMMUNOGENICITY

The analysis of immunogenicity will be performed on the per protocol population as the primary analysis and the full analysis population as a secondary analysis. Analyses described below will be summarized in the interim analyses for all subjects included in the first phase of the study. Relative endpoints derived from Geometric Mean Fold Rise (GMFR) will include all subjects from the per protocol population. Absolute endpoints such as those derived from the Geometric Mean Titer (GMT) will exclude baseline seropositive subjects (i.e., subjects with anti-S IgG antibody titer  $\geq$  LLOQ of the assay at baseline).

Immunogenicity data will be descriptively summarized including the mean, SD, median, range (min and max), GMT, and 95% CI for the GMT with one-half the lower limit of quantification (LLOQ) and with the upper limit of quantification (ULOQ) used as the observed value, whenever these limits are met. For estimation of the GMT, GMT ratio, and corresponding confidence limits, analyses will incorporate censoring where appropriate and log-scale coefficients will be back-transformed in order to compute the estimate and corresponding confidence limits for the relevant quantity. GMFRs will be computed using estimates of the log difference of the paired samples, with corresponding CIs computed via the *t*-distribution, utilizing the antilog transformation to present the ratio. Analyses of binary variables will include 95% CIs computed via the Clopper-Pearson method. Additionally, the distribution of the titers will be summarized using reverse cumulative distribution curves. ([Figure 27](#) through [Figure 32](#)).

The immunogenicity analysis part will be summarized in term of GMT ratio comparing between dose levels and dose with and without adjuvant. The comparing doses of GMT ratio (95% CI) will be performed for the following pairwise: (1) NDV-HXP-S 1  $\mu$ g vs. 3  $\mu$ g, (2) 1  $\mu$ g vs. 10  $\mu$ g, (3) 3  $\mu$ g vs. 10  $\mu$ g, (4) 1  $\mu$ g vs. 1  $\mu$ g+CPG, (5) 3  $\mu$ g vs. 1  $\mu$ g+CPG, (6) 10  $\mu$ g vs. 1  $\mu$ g+CPG.

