## Appendix 1.I. Immunogenicity Analysis - 50% and 80% Neutralizing Antibody (NT50 and NT80)

**Table 90A: Summary of Geometric Mean Titer (GMT) of NT50 against SARS-CoV-2 Pseudovirus in Full Analysis Population**

NT 50 Measure	All (N = 120)	COVIVAC				Placebo (N = 20)
		1 µg (N = 25)	3 µg (N = 25)	10 µg (N = 25)	1 µg + CpG (N = 25)	
Baseline (D1)	GMT (95% CI)	n = xx xx.xx (xx.xx-xx.xx)				
28 days after the first vaccination (D29)	GMT (95% CI)					
14 days after the second vaccination (D43)	GMT (95% CI)					
6 months after the second vaccination (D197)	GMT (95% CI)					

**Note:** GMTs calculation, titers of <10 were assigned as titer of 5.

NT50 GMTs are analyzed from subjects with seronegative anti-S IgG at baseline.

**Table 90A-1: Summary of Geometric Mean Titer (GMT) of NT50 against SARS-CoV-2 Pseudovirus in Full Analysis Population by Age Group**

NT 50 Measure	All (N = 120)	COVIVAC				Placebo (N = 20)
		1 µg (N = 25)	3 µg (N = 25)	10 µg (N = 25)	1 µg + CpG (N = 25)	
Baseline (D1)	18-39 yr.    GMT (95% CI)					
	40-59 yr.    GMT (95% CI)					
28 days after the first vaccination (D29)	18-39 yr.    GMT (95% CI)					
	40-59 yr.    GMT (95% CI)					
14 days after the second vaccination (D43)	18-39 yr.    GMT (95% CI)					
	40-59 yr.    GMT (95% CI)					
6 months after the second vaccination (D197)	18-39 yr.    GMT (95% CI)					
	40-59 yr.    GMT (95% CI)					

**Note:** GMTs calculation, titers of <10 were assigned as titer of 5.

NT50 GMTs are analyzed from subjects with seronegative anti-S IgG at baseline.

**Table 90A-2: Summary of Geometric Mean Titer (GMT) of NT50 against SARS-CoV-2 Pseudovirus in Full Analysis Population by Gender**

NT 50 Measure	All (N = 120)	COVIVAC				Placebo (N = 20)
		1 µg (N = 25)	3 µg (N = 25)	10 µg (N = 25)	1 µg + CpG (N = 25)	
Baseline (D1)	Male	GMT (95% CI)				
	Female	GMT (95% CI)				
28 days after the first vaccination (D29)	Male	GMT (95% CI)				
	Female	GMT (95% CI)				
14 days after the second vaccination (D43)	Male	GMT (95% CI)				
	Female	GMT (95% CI)				
6 months after the second vaccination (D197)	Male	GMT (95% CI)				
	Female	GMT (95% CI)				

**Note:** GMTs calculation, titers of <10 were assigned as titer of 5.

NT50 GMTs are analyzed from subjects with seronegative anti-S IgG at baseline.

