## Appendix 1.J. Immunogenicity Analysis – Anti-S IgG Assessed by ELISA

**Table 110: Summary of Geometric Mean Concentration (GMC) in BAU/mL of Anti-S IgG assessed by ELISA in Full Analysis Population**

Anti-S IgG Measure (BAU/mL)	All (N = 120)	COVIVAC				Placebo (N = 20)
		1 µg (N = 25)	3 µg (N = 25)	10 µg (N = 25)	1 µg + CpG (N = 25)	
Baseline (D1)	GMC (95% CI)					
28 days after the first vaccination (D29)	GMC (95% CI)					
14 days after the second vaccination (D43)	GMC (95% CI)					
6 months after the second vaccination (D197)	GMC (95% CI)					

**Note:** GMCs are analyzed from subjects with seronegative anti-S IgG at baseline.

**Table 110-1: Summary of Geometric Mean Concentration (GMC) in BAU/mL of Anti-S IgG assessed by ELISA in Full Analysis Population by Age Group**

Anti-S IgG Measure (BAU/mL)	All (N = 120)	COVIVAC				Placebo (N = 20)
		1 µg (N = 25)	3 µg (N = 25)	10 µg (N = 25)	1 µg + CpG (N = 25)	
Baseline (D1)	18-39 yr.	GMC (95% CI)				
	40-59 yr.	GMC (95% CI)				
28 days after the first vaccination (D29)	18-39 yr.	GMC (95% CI)				
	40-59 yr.	GMC (95% CI)				
14 days after the second vaccination (D43)	18-39 yr.	GMC (95% CI)				
	40-59 yr.	GMC (95% CI)				
6 months after the second vaccination (D197)	18-39 yr.	GMC (95% CI)				
	40-59 yr.	GMC (95% CI)				

**Note:** GMCs are analyzed from subjects with seronegative anti-S IgG at baseline.

**Table 110-2: Summary of Geometric Mean Concentration (GMC) in BAU/mL of Anti-S IgG assessed by ELISA in Full Analysis Population by Gender**

Anti-S IgG Measure (BAU/mL)	All (N = 120)	COVIVAC				Placebo (N = 20)
		1 µg (N = 25)	3 µg (N = 25)	10 µg (N = 25)	1 µg + CpG (N = 25)	
Baseline (D1)	Male	GMC (95% CI)				
	Female	GMC (95% CI)				
28 days after the first vaccination (D29)	Male	GMC (95% CI)				
	Female	GMC (95% CI)				
14 days after the second vaccination (D43)	Male	GMC (95% CI)				
	Female	GMC (95% CI)				
6 months after the second vaccination (D197)	Male	GMC (95% CI)				
	Female	GMC (95% CI)				

**Note:** GMCs are analyzed from subjects with seronegative anti-S IgG at baseline.

**Table 111: Summary of Geometric Mean Concentration (GMC) in BAU/mL of Anti-S IgG assessed by ELISA in Per Protocol Population**

Anti-S IgG Measure (BAU/mL)	All (N = 120)	COVIVAC				Placebo (N = 20)
		1 µg (N = 25)	3 µg (N = 25)	10 µg (N = 25)	1 µg + CpG (N = 25)	
Baseline (D1)	GMC (95% CI)					
28 days after the first vaccination (D29)	GMC (95% CI)					
14 days after the second vaccination (D43)	GMC (95% CI)					

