**Table 119-2: Percentage of Subjects with Seroresponses in Anti-S IgG Concentration in BAU/mL assessed by ELISA as defined by a  $\geq$  10-fold Increase from Baseline in Per Protocol Population by Gender**

Anti-S IgG Measure $\geq$ 10-fold	All (N = 120)	COVIVAC				Placebo (N = 20)
		1 $\mu$ g (N = 25)	3 $\mu$ g (N = 25)	10 $\mu$ g (N = 25)	1 $\mu$ g + CpG (N = 25)	
28 days after the first vaccination (D29)	Male	n (%) (95% CI)				
	Female	n (%) (95% CI)				
14 days after the second vaccination (D43)	Male	n (%) (95% CI)				
	Female	n (%) (95% CI)				
6 months after the second vaccination (D197)	Male	n (%) (95% CI)				
	Female	n (%) (95% CI)				

**Note:** The 95% CIs were computed via the Clopper-Pearson method.

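### Section 6.4 leaves the stratification factors out of the GMT-ratio intervals, and its ban on subgroup analyses conflicts with 64 age and sex tables in Appendix 1

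*SAP*

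**What the plan says.** Section 4.4 of the SAP: "Randomization will be stratified by gender and age (less than 40 years old and 40 to 59 years old"; the two factors give four strata of about 25% each. The same section gives the purpose: "to ensure the down-selection of formulations is not biased by differences in demographic characteristics of the groups".

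Section 6.4, in full, says "No covariates will be used in the analyses. No subgroup analyses will be performed in Phase 1". It gives no reason for either rule.

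Section 9 sets out the comparison: "The immunogenicity analysis part will be summarized in term of GMT ratio comparing between dose levels and dose with and without adjuvant". It lists six pairwise ratios with 95% CIs among the four active formulations, and says that their estimation takes censoring into account.

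Appendix 1.I opens its subgroup series with "Table 90A-1: Summary of Geometric Mean Titer (GMT) of NT 50 against SARS-CoV-2 Pseudovirus in Full Analysis Population by Age Group", and Appendix 1.J continues it with "Table 110-1: Summary of Geometric Mean Concentration (GMC) in BAU/mL of Anti-S IgG assessed by ELISA in Full Analysis Population by Age Group". The last of the series is the sex version that begins "Table 119-2: Percentage of Subjects with Seroresponses in Anti-S IgG Concentration in BAU/mL assessed by ELISA". Section 6.6.1 lists Tables 90 to 119 for the interim report, whose results are to help choose the formulations for Phase 2.

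**The concern.** Two separate things look wrong.

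First, the trial stratifies by two factors to protect the formulation comparison, then forbids using them in that comparison. If a stratification factor is prognostic, stratified allocation removes most of its contribution from the difference between arms. An unadjusted interval still counts that contribution as residual noise, so it is wider than the design warrants. Balance is also not exact in the data analysed: 25 per arm does not divide by four strata, the primary population is per protocol (section 6.3.5), GMTs drop subjects who are seropositive at baseline (section 9), and missing results are not imputed (section 6.5).

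Second, a programmer cannot follow both section 6.4 and Appendix 1. If Appendix 1 is followed, the interim report carries half-arm results for every immunogenicity measure, with nothing said about how they may be used.

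**Working it through.** **The plan's own figure.** Section 5 claims 90% power to advance a candidate with a true seroresponse rate of 85%, under the rule that the exact 95% lower limit is at least 52%. With the 22 evaluable subjects per candidate that section 5 assumes elsewhere, 16/22 has a lower limit of 49.8% and 17/22 has 54.6%, so 17 responders are needed. P(X ≥ 17 | 22, 0.85) = 0.900, so the figure reproduces. The rule uses NT80 seroresponse counts only; a covariate in a GMT-ratio model cannot change it.

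**Table count.** Parent tables 90A, 90B, 91A, 91B, 92A, 93A, 94–97, 98A, 99A, 100, 101, 102A, 103A, 104, 105, 106A, 107A, 108 and 109 make 22. Tables 110–119 make 10. Total 32, each with an age (-1) and a sex (-2) version: 32 × 2 = 64.

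**Interval width.** Inputs from section 5: log10 SD 0.5 and n = 22 per candidate. Assumed: the share R² of log10-titre variance explained by age stratum and sex.

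- Unadjusted half-width on the log10 scale: t(42) × 0.5 × √(2/22) = 0.304, a factor of 10^0.304 = 2.01 either way.
- Adjusted, with two further terms: t(40) × 0.5 × √(2/22) × √(1 − R²).

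| Assumed R² | Half-width | CI factor | Relative to unadjusted |
|---|---|---|---|
| 0 | 0.305 | 2.02 | 1.00 |
| 0.05 | 0.297 | 1.98 | 0.98 |
| 0.10 | 0.289 | 1.95 | 0.95 |
| 0.20 | 0.273 | 1.87 | 0.90 |

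**Does the unadjusted interval reflect the design?** Trials were simulated with 25 per arm in near-balanced strata, 3 lost at random per arm, R² shared equally between age and sex, and 6,000 trials per setting. The formula behind the unadjusted interval gives a standard error of 0.5 × √(2/22) = 0.151. The simulated SD of the unadjusted log10 difference was 0.151 at R² 0, 0.143 at 0.10 and 0.136 at 0.20. The overstatement is absent at R² 0 and is clear by 0.20.

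**Selection.** In the same simulation, one candidate is truly better and the other three are equal, which is the configuration in section 5. Probability that the best candidate is in the top two:

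| Advantage | R² | Unadjusted | Adjusted |
|---|---|---|---|
| 1.5-fold | 0.05 | 0.918 | 0.920 |
| 1.5-fold | 0.10 | 0.921 | 0.923 |
| 1.5-fold | 0.20 | 0.935 | 0.939 |
| 2-fold | 0 to 0.20 | about 0.99 | about 0.99 |

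**Noise in the half-arm tables.** With 22/2 = 11 per half-arm, the half-width is t(20) × 0.5 × √(2/11) = 0.445, a factor of 2.78 against 2.01 for the whole arm. At a 1.5-fold advantage, the best candidate ranks in the top two in 83% of single strata against 92% overall. With no true age interaction, at least one age stratum shows a different top two from the whole data in about 76% of trials. Much of that 76% is a swap among the three equal candidates for second place, so it measures instability of the display and not the rate of wrong choices.

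**The case against.** The strongest defence is that stratification already does what section 4.4 asks of it. It balances the groups, selection ranks GMTs without testing differences (section 6.8), and the seroresponse gate is separate. Omitting covariates is then a permissible simplification for a secondary endpoint. This stands as far as selection goes: the gain there is under 0.5 percentage points. It does not explain why intervals from a stratified design should ignore the strata, and section 6.4 offers no reason.

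The precision gain also rests on an R² that the SAP does not give. That stands. If age and sex are not prognostic, adjustment gains nothing and costs two degrees of freedom.

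The count of 64 overstates the distinct content. The 32 parents are 16 measures in two populations, and the NT50 concentration is the NT50 titre divided by 1.872, which leaves 15 measures × 2 factors = 30 distinct displays. This is fair, but the conflict with section 6.4 is the same for 30 as for 64.

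A reader might infer that subgroup noise drives down-selection. The documents do not support that. Section 4.1 bases selection on results for whole treatment groups. The discretionary factors it names are relative functional immunogenicity, dose sparing, cost and adjuvant supply. The interim report also contains all 32 whole-group tables. What remains is a risk: the subgroup tables fall within the listed range, and section 5 lets the sponsor weigh other factors.

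Finally, a simple linear model could do harm. Section 9 calls for censoring, and placebo titres may lie largely below the quantification limit (an assumption). A model that ignored censoring, or pooled its variance with placebo, could misstate the ratios between active groups. This stands and shapes the fix.

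**Conclusion.** The point holds in two parts. The contradiction between section 6.4 and Appendix 1 is documentary and needs no assumption: 64 tables are specified that section 6.4 says will not be produced, and section 6.6.1 sends them to the interim report. The omission of the strata from the GMT-ratio intervals is a design mismatch of modest and conditional size: about 0, 2, 5 or 10% narrower intervals at an assumed R² of 0, 0.05, 0.10 or 0.20, with SD 0.5 and 22 per arm. It barely touches the GMT ranking and leaves the NT80 gate alone. Both parts should be corrected; neither invalidates the selection rule.

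Two stronger readings are not supported. One is that the planned intervals are too wide whatever the data show; that is so only if age or sex is prognostic. The other is that the aim to show that the vaccine will "elicit a measurable and dose-dependent neutralizing antibody response" goes unanalysed. Placebo columns with 95% CIs appear in the GMT, fold-rise and seroresponse tables, and the 1 vs 3, 1 vs 10 and 3 vs 10 µg ratios address dose. A trend contrast would be a preference, not the repair of an error.

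**What to change.** Rewrite section 6.4 in two parts.

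1. GMT and GMC ratios among the four active formulations come, at each time point, from a log10-titre (or log10-concentration) model with formulation, age stratum (under 40, 40 to 59) and sex. The censoring stated in section 9 is kept. The unadjusted ratio is reported as a sensitivity analysis.
2. Either delete the -1 and -2 tables from Appendix 1, or state that they are descriptive, have no role in formulation selection and are left out of the interim report. In the second case, section 6.6.1 should list the whole-group tables only.

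The cost is SAP wording and two model terms. With four arms of 22, residual degrees of freedom go from 88 − 4 = 84 to 88 − 6 = 82. No sample size, visit, assay or selection threshold changes.
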